6.7.4.3 Febrile neutropenia

Patients experiencing febrile neutropenia with significant symptoms should be managed in a hospital setting according to standard procedures, with the urgent initiation of IV antibiotic therapy. Patients with febrile neutropenia without symptoms should be managed according to standard guidelines.

6.8 Study governance and oversight

A Safety Review Team (SRT) will be established by Sarah Cannon for this study. Reviewers may include the study PI, Medical Monitor, Lead Biostatistician, Safety Director, Safety Lead, Clinical Data Analyst, Clinical Project Manager, and Sponsor representatives. The roles and responsibilities of the SRT and the Medical Monitor are described in the Dose Escalation Plan.

Once there are at least 3 evaluable patients (see Section 7.2.4) at a dose level the SRT will review and assess all available safety data and any other relevant data from the cohort to make a decision on how the study should proceed. Any dose interruptions and reductions will be taken into account. When available, emerging PK data for plasma exposure and safety will be evaluated to inform the dose escalation or dosing regimen decisions.

The decision may be to:

3. Proceed with dose escalation – refer to Section 7.2.1
4. Expand the cohort to a maximum of 6 evaluable patients
5. De-escalate the dose either to a previous lower dose level (up to a maximum of 6 evaluable patients) or to an intermediate lower dose level
6. Stop the dose escalation part of the study
7. Evaluate alternative dosing schedules.

When there are other patients that are ongoing at the time of this review, the SRT may decide to defer their decision until these further patients become evaluable.

Any patient started on treatment in error, as he/she failed to comply with all of the eligibility criteria but meets the criteria of an evaluable patient, will be reviewed on a case by case basis by the SRT to determine if the patient should be included or excluded in the evaluation of dose escalation.

The decisions and decision-making of the SRT on the next dose level will be documented and provided to the Investigators prior to dosing any new patients.

The timing and frequency of safety evaluations may be revised, in consultation with the SRT, in response to emerging data.

7. INVESTIGATIONAL PRODUCT AND OTHER TREATMENTS

7.1 AZD1775

Investigational product	Dosage form and strength
AZD1775	25 mg and 100 mg plain capsules* 50 mg, 75 mg and 100 mg printed capsules*

*Other dosage form(s) and/or strength(s) may also be used if necessary due to dosage adjustments and/or supply

Plain and printed capsule formulations must not be combined to provide a patient dose. Patients receiving the plain capsule formulation will continue to receive the plain capsule strengths, while those receiving the printed capsule formulation will continue to receive the printed capsule strength. AZD1775 should be taken with 8 ounces of water approximately 2 hours before or 2 hours after food. If a patient misses one of the two daily doses according to schedule, the dose should be taken as soon as possible, but not more than 6 hours after the missed dose was scheduled. If greater than 6 hours, the missed dose should be skipped and the patient should take the next dose when scheduled.

If vomiting occurs after a patient takes the AZD1775 dose, the patient should be instructed not to retake the dose, but to wait until the next scheduled dose of AZD1775. If no dose is scheduled for the following day, the dose will not be 'made up'. If vomiting persists, the patient should contact the Investigator.

7.2 AZD1775 treatment regimen

7.2.1 Dose escalation guidelines

The MTD of AZD1775 monotherapy (dose to be determined) PO QD or BID (for the patients already enrolled on the BID schedule) when administered on a 5/9 Dosing Schedule every 14 days (dosing on days 1 to 5, followed by no treatment on days 6-14), a 5/2 Dosing Schedule every 21 days (dosing on days 1 to 5, no treatment on days 6-7, then dosing again on days 8 to 12, followed by no treatment on days 13-21), or a 5/2 weekly dosing schedule every 21 days (dosing on days 1 to 5, no treatment on days 6-7, dosing on days 8 to 12, no treatment on days 13-14, dosing on days 15 to 19, followed by no treatment on days 20-21) will be defined in this dose escalation phase. Treatment cycles are 14 or 21 days. Patients will continue to receive

treatment with AZD1775 until disease progression, intolerable toxicity, or discontinuation criteria have been met.

Initially, 3 patients will be enrolled and treated at the start of each cohort. However, to allow for any unforeseen discontinuations before the dose-limiting toxicity (DLT) period is completed, an extra patient may be enrolled and treated at each dose escalation cohort. Therefore, there may be a total of 4 patients (3 + 1) at the start of each cohort, provided that the 4th patient is able to start the first day of dosing within approximately 1 week of the 3rd patient in the same dose escalation cohort.

The DLT evaluation period will be 21 days (for patients on both QD 5/2 Schedules, and the BID dosing Schedule) or 28 days (for patients on the QD 5/9 Schedule). If there is 1 DLT out of the first 3-4 DLT-evaluable patients, then further patients will be enrolled and treated to a total of 6 patients. Two DLTs out of 6 evaluable patients will have exceeded the maximum tolerated dose.

The AZD1775 dose levels to be evaluated are presented in [Table 12](#). It may be permitted to escalate the dose in either of the QD dosing regimens, from dose level 1 to dose level 3, without exploring dose level 2, as long as it has been agreed to by the SRT upon reviewing all relevant safety and PK data up to that point. Any intermediate dosing may also be explored. Evaluable patients are those who meet the minimum treatment and safety evaluation requirements of the study (see [Table 2](#), [Table 3](#), and [Table 4](#)) and/or those who experience a DLT during Cycle 1 and/or Cycle 2.

Table 12 AZD1775 Dosing Cohorts

Cohort	AZD1775	Number Patients
BID1	125 mg PO BID ^{a,b}	3-6 patients (completed)
BID 2	150 mg PO BID ^{a,b}	3-6 patients (completed)
QD 1.1 and QD 1.2	200 mg PO QD ^{c,d,e,f}	3-6 patients in each dosing schedule
QD 2.1, QD 2.2, and QD 2.3	250 mg PO QD ^{c,d,e,f}	3-6 patients in each dosing schedule
QD 3.1, QD 3.2, and QD 3.3	300 mg PO QD ^{c,d,e,g}	3-6 patients in each dosing schedule
QD 4.1, and QD 4.2	400 mg PO QD ^{c,d,g}	3-6 patients in each dosing schedule

^a AZD1775 taken in 12-hour intervals

^b AZD1775 taken Days 1-5; Rest, i.e., no treatment Days 6-14

^c Cohorts QD 1.1, 2.1, 3.1, and 4.1-5/9 schedule: Dosing on days 1 to 5, every 14 days (no treatment on days 6-14)

^d Cohorts QD 1.2, 2.2, 3.2, and 4.2-5/2 schedule : Dosing on days 1 to 5, and days 8 to12, every 21 days (no treatment on days 6-7 and 13-21)

^e Cohorts QD 2.3 and 3.3-5/2 weekly schedule : Dosing on days 1 to 5, days 8 to 12, and days 15-19 every 21 days (no treatment on days 6-7, 13-14, and 20-21)

^f May be evaluated in 5/9 (Cohorts QD 1.1 and 2.1), 5/2 (Cohorts 1.2, and 2.2), and 5/2 weekly (Cohort 2.3) regimens in parallel as shown in [Figure 4](#)

^g May be evaluated in 5/9 (Cohorts QD 3.1, and 4.1), 5/2 (Cohorts 3.2 and 4.2), and 5/2 weekly (Cohort 3.3) regimens in parallel if considered appropriate.

Dose escalation will occur in accordance with the following rules:

- Up to 6 patients will be enrolled and treated in each cohort, and must be deemed evaluable.
- If one of the first 3 patients enrolled and treated in a given cohort experiences a DLT, at least 3 additional patients will be enrolled in that cohort.
- If less than one-third of evaluable patients in a given cohort experiences a DLT (i.e., fewer than 0 of 3 or 1 of 6), escalation may proceed to the next higher dose level.
- If a DLT is observed in one-third or more of evaluable patients (e.g., 2 or more of up to 6 evaluable patients), the dose at which this occurs will be considered not tolerated, and the MTD will have been exceeded.
- The highest dose level(s) at which less than one-third of evaluable patients (0 of 3 patients or 1 of 6 patients) experience a DLT will be declared the MTD.
- Dose escalation will continue until identification of the MTD.
- Intra-patient dose escalation is not permitted.

Alternative dose levels, cohorts and/or schedules which may include reductions of dose interval treatment schedules may be guided by PK or PDx evaluations as well as tolerability and may be evaluated before the MTD/RP2D is defined. Modified PK assessments would be defined to accommodate the investigation of alternative dose levels and/or schedules.

The AZD1775 monotherapy dose will be selected by the SRT upon review of the safety and PK data.

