2. STUDY OBJECTIVES

2.1 Primary objective

Primary Objective:	Outcome Measure:
To determine the MTD/RP2D of AZD1775 monotherapy administered QD (schedule 5/9, 14-day cycle or schedule 5/2, 21-day cycle) or BID (5/9 schedule, 14-day cycle) in patients with locally advanced or metastatic solid tumours.	The number and incidence of DLTs in the first cycle (21 days) of the QD 5/2 schedule, and the number and incidence of DLTs in the first 2 cycles (28 days) of the QD or BID 5/9 schedule.

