7.2.2 Dose-limiting toxicity

Dose-limiting toxicities will be evaluated during the first 28 days (5/9 Schedule), or first 21 days (both 5/2 Schedules) of AZD1775 monotherapy treatment. If appropriate the DLT observation period can be extended by up to 2 weeks in case of treatment delay due to study drug-related AE. Toxicity will be graded according to the NCI CTCAE v4.03.

Patients must complete Cycle 1 (i.e. 21 days on either 5/2 schedule) or Cycle 1 and Cycle 2 (i.e. 28 days on the 5/9 schedule) safety evaluations and must receive at least 80% of the planned dose to be considered evaluable. Patients receiving less than 80% of Cycle 1 dose (21 days for the 5/2 schedule) or Cycle 1 and Cycle 2 dose (28 days for the 5/9 Schedule) will be replaced unless they experienced a DLT confirmed by the SRT.

Dose-limiting toxicities are defined as any of the following toxicities not attributable to the disease or disease-related process under investigation, that occur from the first dose of study treatment up to the last day of Cycle 2 (first 28 days) for the 5/9 Schedule, or the last day of Cycle 1 (first 21 days) for the 5/2 Schedule, and that meet at least 1 of the criteria below:

1. Haematologic toxicity \geq Grade 4 for more than 7 days including infection with febrile neutropenia
2. Grade 3 thrombocytopenia associated with Grade ≥ 2 bleeding
3. Haematologic toxicity \geq Grade 4 neutropenia or thrombocytopenia for more than 7 days, or Grade 4 Infection with febrile neutropenia, or Grade 3 neutropenic fever, or Grade 3 thrombocytopenia associated with Grade ≥ 2 bleeding.
4. Non-haematologic toxicity \geq Grade 3
5. Liver function tests (LFTs), Grade ≥ 3 total bilirubin, hepatic transaminase ALT or AST or ALP lasting >48 hours, or any change in liver functions tests consistent with Hy's Law (see [Appendix D](#).)
6. Any other toxicity that is clinically significant and/or unacceptable that does not respond to supportive care, results in a disruption of dosing schedule of more than 7 days, or is judged to be a DLT by the investigator in collaboration with the medical monitor.

A DLT excludes:

- Nausea, vomiting, or diarrhoea that responds to supportive care
- Isolated laboratory change of any grade without clinical sequelae or clinical significance
- Alopecia of any grade

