7.2.4 Determination of MTD/RP2D

The patient population used to determine the MTD/RP2D will consist of patients who have met the minimum safety evaluation requirements of the study, and/or who have experienced a DLT from the first dose of study treatment up to the last day of Cycle 2 (first 28 days) for the 5/9 Schedule, or the last day of Cycle 1 (first 21 days) for either 5/2 Schedule. Minimum safety requirements will be met if during Cycle 1 (for both 5/2 Schedules) and Cycles 1 and 2 (for the 5/9 Schedule) of treatment the patient receives a minimum of 80% of treatment doses of AZD1775, completes the safety evaluations (see [Table 2](#), [Table 3](#), and [Table 4](#)), and is observed for at least 28 days. Patients who do not meet these minimum safety evaluation and treatment requirements and who do not experience a DLT will be replaced.

Treatment dose will be considered non-tolerated and dose escalation will cease if 2 or more of 6 evaluable patients experience a DLT at a dose level.

A minimum of 12 patients will be treated at the MTD/RP2D. More than one dose level may be expanded with up to 12 patients per dose level to get further experience with the dosing schedule with AZD1775.

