8.2.4 Dose-limiting toxicity analysis set

The DLT Analysis Set will include all patients in the dose escalation phase who received at least 80% of the AZD1775 dose and completed the minimum safety evaluation requirements during the first 28 days (5/9 Schedule) or 21 days (either 5/2 Schedule) of treatment or who experienced a DLT during the first 28 days (5/9 Schedule) or 21 days (either 5/2 Schedule) of treatment regardless of the amount of drug received.

The patients in the DLT analysis set will be used for the determination of the MTD of AZD1775.

Refer to the SAP for additional information.

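### The DLT window for BID patients (21 or 28 days) and the observation needed for 5/2 patients to be evaluable (21 or 28 days) differ between sections, so the primary endpoint has no single definition

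*Protocol*

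**What the plan says.** **BID.** The primary outcome in Section 2.1, repeated in the synopsis, includes "the number and incidence of DLTs in the first 2 cycles (28 days) of the QD or BID 5/9 schedule". Section 7.2.1 says otherwise: "The DLT evaluation period will be 21 days (for patients on both QD 5/2 Schedules, and the BID dosing Schedule". Section 7.2.2 names only the two schedule types: "Dose-limiting toxicities will be evaluated during the first 28 days (5/9 Schedule), or first 21 days (both 5/2 Schedules) of AZD1775 monotherapy treatment". BID is a 5/9 regimen: Table 12, note b, gives "AZD1775 taken Days 1-5; Rest, i.e., no treatment Days 6-14".

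**5/2 schedules.** Sections 2.1, 7.2.1 and 7.2.2 use 21 days. Section 8.2.4 builds the DLT Analysis Set from patients who, besides meeting the 80% dose rule, "completed the minimum safety evaluation requirements during the first 28 days (5/9 Schedule) or 21 days (either 5/2 Schedule) of treatment", or who had a DLT in that time. Section 7.2.4 separates the schedules when it states the dosing requirement. It then adds, for everyone, "and is observed for at least 28 days", and replaces DLT-free patients who fall short.

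**Who uses which rule.** Section 6.8 sends the Safety Review Team (SRT) to Section 7.2.4 for the meaning of an evaluable patient. Section 8.2.4 says its own set determines the MTD, and Section 8.4.3 uses that set for the DLT summary.

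**The concern.** In a 3+3 design the DLT window decides which events count, and the evaluability rule decides which patients do. Both must be fixed for each schedule, because cohorts hold 3 to 6 patients and the tolerability limit is one-third. Here the BID patients carry two windows, and the 5/2 patients carry two tests of whether they count. The SRT's decision and the reported DLT table could then rest on different events (BID) or different patients (5/2), with nothing in the protocol to say which section prevails.

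**Working it through.** **1. Reproduce the plan's windows.** Cycles × cycle length: 5/9 is 2 × 14 = 28 days; 5/2 is 1 × 21 = 21 days. Both match Section 2.1. The BID window in 7.2.1 is 21 / 14 = 1.5 cycles, which is not a whole number of cycles.

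**2. Set the sections side by side (days).**

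| Section | BID | QD 5/9 | QD 5/2 |
|---|---|---|---|
| 2.1 and synopsis | 28 | 28 | 21 |
| 7.2.1 | **21** | 28 | 21 |
| 7.2.2 | 28 (as 5/9) | 28 | 21 |
| 7.2.4, DLT window | 28 (as 5/9) | 28 | 21 |
| 7.2.4, minimum observation | 28 | 28 | **28** |
| 8.2.4 | 28 (as 5/9) | 28 | 21 |

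The bold cells are the outliers.

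**3. BID: what the missing week holds.** Planned dosing is on Days 1-5 and 15-19, twice daily: 10 days × 2 = 20 doses under either window. Follow-up after the last dose is 21 − 19 = 2 days or 28 − 19 = 9 days. Section 7.2.2 counts Grade 4 haematologic toxicity only if it lasts more than 7 days. An event starting on Day d can reach W − d + 1 days inside a window of W days.
- W = 21: 21 − d + 1 > 7 requires d ≤ 14, so no event starting in the second course (Day 15 on) can qualify.
- W = 28: 28 − d + 1 > 7 requires d ≤ 21, so events starting on Days 15-21 can qualify.

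This takes the duration as having to be reached inside the window. If onset alone decides, the windows still differ for onsets on Days 22-28. The Cycle 2 Day 8 haematology and AE check in Table 2 falls nominally on Day 14 + 8 = 22, one day outside the shorter window.

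**4. BID: illustrative size.** The documents give no DLT risk by day. Assume a constant hazard, p21 = 1 − (1 − p28)^(21/28), and a 3+3 escalation probability of (1 − p)³ + 3p(1 − p)²(1 − p)³.

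| 28-day risk | 21-day risk | Chance of escalating, 28 days | Chance of escalating, 21 days |
|---|---|---|---|
| 20% | 15% | 71% | 81% |
| 30% | 24% | 49% | 63% |
| 40% | 32% | 31% | 46% |

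Constant hazard is a rough assumption, since all planned doses fall by Day 19.

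**5. 5/2: who falls between the rules.** Take a patient with at least 80% of the dose, complete safety evaluations to Day 21, no DLT, and last observed on Days 22-27. Sections 7.2.2 and 8.2.4 count this patient; 7.2.4 replaces the patient. In a cohort of 3, the SRT then has 3 − 1 = 2 evaluable patients and its trigger of at least 3 in Section 6.8 is not met. In a cohort of 6 with one such replacement, the SRT sees 6 patients and the Section 8.2.4 table holds 6 + 1 = 7. Two DLTs would be 2/6 = 33.3% (at the one-third limit) or 2/7 = 28.6% (below it).

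**The case against.** The strongest reply is that little now turns on this. Table 12 marks both BID cohorts as completed, and Tables 2-4 are all headed as closed to enrolment, so no future escalation depends on the BID sentence. For reporting, Section 8.4.3 points to one set (8.2.4), whose 5/9 window covers BID and agrees with Section 2.1. The 5/2 gap is narrow too. Section 6.3.1 collects AEs until 30 days after the last dose, so from a Day 12 or Day 19 last dose to about Day 42 or 49. Only death, loss to follow-up, withdrawal of consent or (Section 4.3.1) new cancer therapy on Days 22-27 would separate the definitions. All of this stands. It limits the effect but does not remove the contradiction.

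Section 1.3 does mention BID under a 5/2 schedule, which might seem to explain the 21 days. Table 12 and Figure 2 list no such cohort; both BID cohorts are 5/9.

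Two stronger readings are tempting and are not supported:
- **A Day-42 window on 5/2.** Section 7.2.1 counts as evaluable "those who experience a DLT during Cycle 1 and/or Cycle 2" without naming a schedule. But DLT is a defined term, and Sections 7.2.2, 7.2.3 and 7.2.4 end it at Day 21 on 5/2. The phrase is loose drafting, not a third window.
- **Expansion patients wrongly dropped.** Section 8.2.4 covers "all patients in the dose escalation phase who received at least 80% of the AZD1775 dose", while 7.2.4 does not mention phase. Section 7.2.4 never says that expansion patients count, and restricting the set to escalation patients fits a 3+3 MTD. All 12 patients at the MTD/RP2D are in the full-analysis-set safety summaries (8.2.2, 8.4.3). This is a choice of scope, not a conflict.

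**Conclusion.** The plan is wrong as written on two counts: the BID window in 7.2.1 against 2.1, 7.2.2, 7.2.4 and 8.2.4, and the 28-day minimum in 7.2.4 for patients whose window is 21 days. Both bear on the primary endpoint, so they are more than clerical.

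BID numerators and 5/2 denominators need not agree between sections. Whether they do differ depends on events or losses falling in the disputed days, which the protocol cannot show. A reader might infer that the MTD is wrong or that a live dosing decision is at risk; the documents support neither. The effect is mainly on the reported primary outcome and on the support for the MTD. The 5/2 discrepancy is confined to DLT-free, adequately dosed patients last observed on Days 22-27. The percentages in step 4 rest on assumed risks and a constant hazard; the conflict itself rests on no assumption beyond reading BID as a 5/9 schedule, as Section 2.1 and Table 12 do.

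**What to change.** Reconcile the passages so that one DLT window per schedule appears in the same words in Sections 2.1, 7.2.1, 7.2.2, 7.2.4 and 8.2.4, with BID named explicitly. The primary outcome and the DLT Analysis Set already agree with each other, so the passages to resolve are the BID window in 7.2.1 and the 28-day minimum in 7.2.4 as it applies to 5/2. Make the 7.2.4 observation minimum schedule-specific, so that the evaluability rule the SRT uses through Section 6.8 matches 8.2.4. As a tidy-up, tie the Cycle 1 and Cycle 2 phrase in 7.2.1 to the schedule-specific window.

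The cost is wording, and possibly a re-review of BID Days 22-28, a period that the Table 2 visits already cover. The sample size does not change.

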7.2.2 Dose-limiting toxicity

Dose-limiting toxicities will be evaluated during the first 28 days (5/9 Schedule), or first 21 days (both 5/2 Schedules) of AZD1775 monotherapy treatment. If appropriate the DLT observation period can be extended by up to 2 weeks in case of treatment delay due to study drug-related AE. Toxicity will be graded according to the NCI CTCAE v4.03.

Patients must complete Cycle 1 (i.e. 21 days on either 5/2 schedule) or Cycle 1 and Cycle 2 (i.e. 28 days on the 5/9 schedule) safety evaluations and must receive at least 80% of the planned dose to be considered evaluable. Patients receiving less than 80% of Cycle 1 dose (21 days for the 5/2 schedule) or Cycle 1 and Cycle 2 dose (28 days for the 5/9 Schedule) will be replaced unless they experienced a DLT confirmed by the SRT.

Dose-limiting toxicities are defined as any of the following toxicities not attributable to the disease or disease-related process under investigation, that occur from the first dose of study treatment up to the last day of Cycle 2 (first 28 days) for the 5/9 Schedule, or the last day of Cycle 1 (first 21 days) for the 5/2 Schedule, and that meet at least 1 of the criteria below:

1. Haematologic toxicity \geq Grade 4 for more than 7 days including infection with febrile neutropenia
2. Grade 3 thrombocytopenia associated with Grade ≥ 2 bleeding
3. Haematologic toxicity \geq Grade 4 neutropenia or thrombocytopenia for more than 7 days, or Grade 4 Infection with febrile neutropenia, or Grade 3 neutropenic fever, or Grade 3 thrombocytopenia associated with Grade ≥ 2 bleeding.
4. Non-haematologic toxicity \geq Grade 3
5. Liver function tests (LFTs), Grade ≥ 3 total bilirubin, hepatic transaminase ALT or AST or ALP lasting >48 hours, or any change in liver functions tests consistent with Hy's Law (see [Appendix D](#).)
6. Any other toxicity that is clinically significant and/or unacceptable that does not respond to supportive care, results in a disruption of dosing schedule of more than 7 days, or is judged to be a DLT by the investigator in collaboration with the medical monitor.

A DLT excludes:

- Nausea, vomiting, or diarrhoea that responds to supportive care
- Isolated laboratory change of any grade without clinical sequelae or clinical significance
- Alopecia of any grade

Cycle 1 (for both 5/2 schedules) and Cycle 1 and Cycle 2 (for the 5/9 schedule) data for each cohort will be reviewed by an SRT after completion of each dose level cohort. Participating sites will be informed of the findings and of the next cohort to be evaluated as soon as possible.

